7.3.2.2 Classification of CML subjects

Subjects will be classified as per the NCCN guidelines for Chronic Myeloid Leukaemia¹³ as follows

Table 7-2 Classification of Subjects with CML

| CML Phase | Criteria |
|-------------------|--|
| Chronic Phase | $< 15\%$ blasts in peripheral blood or bone marrow and $< 20\%$ basophils in peripheral blood and $< 30\%$ (blasts + promyelocytes) in peripheral blood or bone marrow and $> 100 \times 10^9$ platelets/L in peripheral blood and No extra-medullary disease |
| Accelerated Phase | $\geq 15 - < 30\%$ blasts in peripheral blood or bone marrow or $\geq 20\%$ basophils in peripheral blood or bone marrow or $\geq 30\%$ (blasts + promyelocytes) in peripheral blood or bone marrow (but $< 30\%$ blasts) or $\leq 100 \times 10^9$ platelets/L in peripheral blood unrelated to therapy or Additional clonal cytogenetic abnormalities in Ph+ cells |
| Blast Crisis | $\geq 30\%$ blasts in peripheral blood, bone marrow or both or Extra-medullary disease |

Note: For subjects wherein rapid disease progression is observed (beyond the aforementioned criteria) and subject safety is a concern, the subject can be discontinued at Investigator's discretion in consultation with Sponsor or Sponsor nominated CRO's medical monitor.

7.3.2.3 Criteria for Disease Progression

Table 7-3 Criteria for disease progression of subjects enrolled into the study

| Disease status at enrolment | Disease progression criteria | Reference |
|-----------------------------|--|------------|
| CML-CP | Progression to CML-AP or CML-BP at any time during the study Or WBC count that rises to $> 20.0 \times 10^9 / L$ ($> 20,000 / mm^3$) on two occasions at least 2 weeks apart (after first 4 weeks of K0706 therapy) in a subject Or | [REDACTED] |

| | | |
|---------------|--|------------|
| | Platelet count that rises to $> 600 \times 10^9/L$ ($> 600,000/mm^3$) on two occasions at least 2 weeks apart (after first 4 weeks of K0706 therapy) in a subject Or Loss of CHR (in the absence of a CyR) confirmed by complete blood counts done 4 weeks apart Or Loss of MCyR Or Death | |
| CML-AP | Development of confirmed BP Or Loss of previous major haematological response over a 2 week period Or No decrease from baseline levels in percentage blasts in peripheral blood or bone marrow on all assessments over a 4 week period (monitored at least every week) Or Death | [REDACTED] |
| CML-BP | Increasing blasts in peripheral blood or bone marrow over a 4 week period (monitored at least every week) Or Death | [REDACTED] |

Note: For subjects wherein rapid disease progression is observed (beyond the aforementioned criteria) and subject safety is a concern, the subject can be discontinued at Investigator's discretion

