6.3.2.3 Criteria for Disease Progression

Table 6-2 Criteria for disease progression of subjects enrolled into the study

| Disease status at enrolment | Disease progression criteria | Reference |
|-----------------------------|--|---|
| CML-CP | Progression to CML-AP or CML-BP at any time during the study Or WBC count that rises to $> 20.0 \times 10^9$ /L ($> 20,000/\text{mm}^3$) on two occasions at least 2 weeks apart (after first 4 weeks of K0706 therapy) in a subject Or Platelet count that rises to $> 600 \times 10^9$ /L ($> 600,000/\text{mm}^3$) on two occasions at least 2 weeks apart (after first 4 weeks of K0706 therapy) in a subject Or Loss of CHR (in the absence of a CyR) confirmed by complete blood counts done 4 weeks apart Or Loss of MCyR |  |

| | | |
|----------------------------|---|------------|
| | Or Death | |
| CML-AP | Development of BP Or Loss of previous major haematological response over a 2 week period Or No decrease from baseline levels in percentage blasts in peripheral blood or bone marrow on all assessments over a 4 week period (monitored at least every week) Or Death | [REDACTED] |
| CML-BP/ Ph+ ALL | Increasing blasts in peripheral blood or bone marrow over a 4 week period (monitored at least every week) Or For Ph + ALL, localization of disease at extra-medullary sites necessitating alternative therapy (example: Localization of ALL in breast tissue confirmed by histopathology or alternate methodology including clinical evidence) Or Death | [REDACTED] |

Note: For subjects wherein rapid disease progression is observed (beyond the aforementioned criteria) and subject safety is a concern, the subject can be discontinued at Investigator's discretion

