13.2 APPENDIX II

Anticipated AEs and the risk monitoring methods in the study

| Anticipated AE | Risk Monitoring | Risk Monitoring Measures |
|-----------------|---|---|
| Fluid retention | Monitor subjects for development of signs and symptoms of fluid retention during clinical trial | Information included in the ICF for patient education, Included in the schedule of assessments in the Protocol: Intensive subject monitoring inclusive of physical examination, ECG, biochemistry. If AEs of fluid retention are suspected or detected, the subjects should also be monitored for signs and symptoms and management using supportive therapy may be considered according to standard medical practice, institutional and applicable protocol-specific guidelines. |

| | | |
|---------------------|---|--|
| Myelosuppression | Monitor complete blood counts regularly. | 
Information included in the ICF for patient education
 
Included in the schedule of assessments in the Protocol:
 
Intensive haematology monitoring included in Cycle 1 and 2 at weekly intervals
 
Additional haematology monitoring will be at Investigator's discretion based on subject's clinical condition and standard medical practice, institutional and applicable protocol-specific guidelines.
 |
| Cardiac arrhythmias | 
Monitor subject's vitals, BP, ECG regularly per protocol schedule of assessment
 
Subjects should be advised to report signs and symptoms of slow or rapid heart rate
 | 
Information included in the ICF for patient education
 
Included in the schedule of assessments in the Protocol:
 
Intensive ECG monitoring included in Cycle 1 and 2 at weekly intervals and thereafter at every 3 monthly study visit
 
Additional ECG and conduct of specific cardiac evaluations such as 2D echocardiography will be at Investigator's discretion based on subject's clinical condition and standard medical practice, institutional and applicable protocol-specific guidelines
 
Drugs known to prolong the QT interval and strong CYP3A4 inhibitors should be avoided as per protocol guidance
 
Caution is recommended when administering to subjects with hepatic impairment.
 |
| Heart failure | Subjects should be monitored for signs or symptoms consistent with cardiac dysfunction and should be treated appropriately. | See methods included in Cardiac arrhythmias above |

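### Read literally, the accelerated-phase blast rule makes an AP subject with no baseline blasts progress by week 4, so Cohort B PFS can be misclassified; late blast-phase progression also depends on counts outside the stated schedule

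*Protocol*

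**What the plan says.** **Entry to AP (Protocol 7.3.2.2, Table 7-2).** The AP criteria are alternatives. Besides the blast criteria, a subject qualifies with basophils of 20% or more, with platelets at or below 100 × 10⁹/L ("platelets/L in peripheral blood unrelated to therapy"), or with "Additional clonal cytogenetic abnormalities in Ph+ cells". None of these three requires blasts.

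**Progression (Protocol 7.3.2.3, Table 7-3).** AP has four criteria: "Development of confirmed BP"; "Loss of previous major haematological response over a 2 week period"; "No decrease from baseline levels in percentage blasts in peripheral blood or bone marrow on all assessments over a 4 week period", with monitoring at least weekly; and death. Blast phase (BP) has two: "Increasing blasts in peripheral blood or bone marrow over a 4 week period (monitored at least every week", and death. Part B repeats the AP wording in Table 6-2: "No decrease from baseline levels in percentage blasts in peripheral blood or bone marrow on all assessments".

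**Response (Protocol Appendix I, Table 7-13).** For AP and BP, both components of MaHR (complete haematologic response, CHR, and no evidence of leukaemia, NEL) require no blasts in peripheral blood and basophils below 5%. The Cohort B and C primary endpoint needs two haematological assessments at least 4 weeks apart.

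**Consequence and PFS.** Protocol 7.5.3.1 accepts progression by Section 7.3.2.3 or by investigator judgement, and says progressed subjects should be discontinued. SAP Section 13 counts documented progression requiring withdrawal, or death. It does not cite Table 7-3.

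**Monitoring (Protocol Appendix II).** "Intensive haematology monitoring included in Cycle 1 and 2 at weekly intervals"; the haemorrhage row adds 3-monthly visits after that. Further counts are at the investigator's discretion.

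**The concern.** A criterion based on the absence of a fall carries information only when there is something to fall. For a subject at 0% blasts it is met whatever the drug does. The same blood counts can then satisfy a progression criterion in Table 7-3 and the response criteria in Appendix I.

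Progression should lead to discontinuation, and the SAP counts progression that requires withdrawal, so a literal call passes straight into PFS, a secondary endpoint in all subjects. It can also reach the Cohort B primary endpoint: a subject taken off at week 4 may never have the second assessment that confirms MaHR.

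In BP the risk runs the other way. The only criterion besides death needs weekly counts that the stated monitoring provides for roughly the first two cycles.

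**Working it through.** The documents give no PFS estimate, event count or progression rate, and the inputs in Protocol 7.8.2 are redacted, so there is no planned figure to reproduce. The check is logical; the numbers below are illustrations.

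**1. Who can be blast-free and eligible.** Protocol 7.3.1.4.1 excludes AP subjects already in MaHR. Setting Table 7-2 against Appendix I:

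| AP entry route, no blood blasts or promyelocytes | In MaHR at entry? | Eligible? |
|---|---|---|
| Platelets 20,000–100,000/mm³, otherwise clean counts | Yes (NEL) | No |
| Clonal abnormality, otherwise clean counts | Yes (CHR) | No |
| Basophils 20% or more | No (limit is below 5%) | Yes |
| Clonal abnormality, WBC above normal | No (WBC limit) | Yes |

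The exclusion narrows the group but does not empty it. Appendix I also contains a response rule for subjects who enter in MaHR, which conflicts with the exclusion.

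**2. How often the criterion is met without any change in disease.** Assume the true blast percentage p is constant, each differential counts n cells, and four weekly counts follow baseline. With X binomial(n, p):

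P(no decrease on all four) = Σₖ P(X = k) · P(X ≥ k)⁴

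| True p | n = 100 | n = 200 |
|---|---|---|
| 0% | 1.00 | 1.00 |
| 1% | 0.43 | 0.32 |
| 2% | 0.32 | 0.28 |
| 20% | 0.23 | 0.22 |

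At 0% it is certain. At p = 1% and n = 100, most of the 0.43 comes from baselines recorded as zero: P(X = 0) = 0.99¹⁰⁰ = 0.366. Among baselines above zero the probability is (0.427 − 0.366)/(1 − 0.366) = 0.10.

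**3. Effect on PFS.** If a share q of Cohort B is blast-free and every such subject is called, 4-week PFS is at most 1 − q: 90%, 80%, 70% and 50% for q = 10%, 20%, 30% and 50%. The documents do not give q.

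**4. Effect on confirmed MaHR.** With the first on-treatment count at week 1, the earliest confirmation is week 1 + 4 = week 5. The literal progression call comes at week 4.

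**5. Weekly counts after Cycle 2.** Weekly counts across 4 weeks mean five counts including the first. Assume 28-day cycles (the length is redacted; 28 days is inferred from the Part B toxicity window) and later visits every 84 or 91 days. Any 28-day window after Cycle 2 then holds 0 or 1 scheduled count. Weekly cover is 56 of about 1,826 days, or 3% of the 60 months. If weekly counting began only at the next scheduled visit, documentation of a blast rise would lag by:

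- 84-day visits: mean 84/(2 × 7) + 4 = 10 weeks; maximum 84/7 + 4 = 16 weeks
- 91-day visits: mean 91/(2 × 7) + 4 = 10.5 weeks; maximum 91/7 + 4 = 17 weeks

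**The case against.** Table 7-3 is not the PFS definition. The SAP requires progression that leads to withdrawal, 7.5.3.1 admits investigator judgement, and 7.3.2.5 says only that a subject may be withdrawn for progression. A sensible investigator would not withdraw a responding subject because zero blasts stayed at zero. This stands as mitigation, and it is why the claim is that PFS can be misclassified. It does not remove the problem, because 7.5.3.1 also says progressed subjects should be discontinued and the SAP does not say which calls count.

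The criterion refers to blood or marrow, so a subject with no blood blasts might have marrow blasts that fall. Whether that defeats the criterion is not stated. The ambiguity supports clarifying the rule.

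A reader might infer that AP progression as a whole needs weekly counts. It does not: confirmed blast phase and loss of MaHR do not depend on them, and the AP blast criterion can be assessed in Cycles 1 and 2.

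A reader might also infer that late BP progression cannot be observed before death. The documents do not support that. Extra counts are permitted, investigator judgement is accepted, and the weekly condition can be read as an instruction to start weekly counts once progression is suspected. The Section 11.2 assessment table is not in the text available, so the schedule point rests on Appendix II.

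**Conclusion.** The contradiction in AP holds on the wording of the tables. An eligible AP subject with no baseline blasts meets a progression criterion by week 4 regardless of treatment effect, possibly while meeting the CHR or NEL count criteria. Cohort B PFS can be misclassified as a result, and confirmation of MaHR can be cut short. In BP, progression after Cycle 2 rests on unscheduled counts or investigator judgement unless Section 11.2 provides more than Appendix II does.

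The size cannot be computed from the documents. It depends on the blast-free share among eligible AP subjects and on how investigators apply the criterion, and neither is given. It is tempting to convert the problem into a shift in median PFS. With an assumed 12-month exponential median and 20% or 40% of the cohort called at about week 4, the apparent median is ln(0.8/0.5)/(ln 2/12) = 8.1 months or ln(0.6/0.5)/(ln 2/12) = 3.2 months. Both inputs are unsourced, and the calculation assumes every blast-free subject is called, so these figures should not be used as estimates. Nor do the documents show that PFS will be wrong in both directions. PFS is secondary and no formal testing is planned (Protocol 7.8), so the stake is interpretation of a reported estimate, plus possible loss of confirmed responders in Cohort B.

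**What to change.** In SAP Section 13, for the PFS derivation only:

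1. State that the criterion on absence of a blast decrease is evaluable only in AP subjects with blasts above 0% at baseline in the compartment assessed (blood or marrow). Assess other AP subjects on the remaining AP criteria.
2. State that blast-based progression is derived from all available counts, scheduled and unscheduled, and dated at the first qualifying count.
3. Add a sensitivity analysis that counts investigator-declared progression.

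The threshold is any blasts above 0%, because a cut-off of 15% would drop AP subjects whose lower but measurable blasts can fall.

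The cost is SAP text and programming, with no new procedures. Later progression dates will be less finely timed, and some noise remains at low non-zero baselines, as the working shows.

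Table 7-3 also drives discontinuation. The clinical team must therefore separately reconcile Tables 7-2 and 7-3, Section 7.5.3.1, Appendix I and Appendix II, together with the matching wording in Table 6-2. No clinical rule is proposed here.

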7.3.2.4 Restrictions

The following restrictions will apply to all subjects during the study.

- Women and men must continue birth control for the duration of the study and at least 3 months after the last administration of IMP. See Section 7.3.2.4.2 for acceptable forms of contraception

- Subjects should refrain from the use of concomitant medications that might reasonably influence the results of the study prior to K0706 administration and at any time during participation in the study. For restrictions regarding the allowed and disallowed medications, see Section 7.4.6.2.
- While K0706 should be preferably taken [REDACTED], the subjects should maintain approximately [REDACTED] IMP dosing throughout the study.

7.3.2.4.1 Avoidance of Pregnancy

Prior to study enrollment, women of childbearing potential (WOCBP) must be advised of the importance of avoiding pregnancy during study participation and the potential risk factors for an unintentional pregnancy.

Pregnancy should be avoided by either true abstinence or the use of 2 effective means of contraception (see Section 7.3.2.4.2) for the duration of the study and a total period of 3 months after the subject has taken the last administration of IMP.

Women of Childbearing Potential

Non-pregnant subjects and subjects of childbearing age must agree to use effective methods of contraception. All WOCBP must practice an effective method of birth control during the course of the study, in a manner such that risk of failure is minimized.

All WOCBP MUST have a negative pregnancy test prior to first receiving IMP. If the pregnancy test is positive, the subject must not receive IMP.

In order to include WOCBP in any clinical study, certain precautions pertaining to pregnancy must be taken. These will include pregnancy testing at Screening, Day 1 of each cycle and the EoT visit.

Female subjects who become pregnant during the study will be withdrawn. If a subject becomes pregnant during the study, the pregnancy will be recorded as a significant medical event and reported per the SAE reporting procedures.

Women of Non-Childbearing Potential

Female subjects of non-childbearing potential are defined as women who had a bilateral oophorectomy/hysterectomy or are postmenopausal, having been amenorrheic for at least 12 months with an appropriate clinical profile, e.g., appropriate age, history of vasomotor symptoms.

Male Subjects

Men enrolled on this study should understand the risks to any sexual partner of childbearing potential and should practice an effective method of birth control.

As there is no information for K0706 being secreted in the ejaculate, male subjects (including men who have had vasectomies) including whose partners are currently pregnant should use barrier method for the duration of the study and a total period of 3 months after the subject has taken the last administration of IMP. This is to ensure that the fetus is not exposed to the IMP in the ejaculate.

There is no information about effects that K0706 could have on the development of the fetus in humans; however, K0706 is a teratogen and induces fetal toxicity in toxicology studies. Therefore, it is important that the partners of male subjects do not become pregnant during the study and for a total period of 3 months after the male subject has received the last administration of IMP.

7.3.2.4.2 Acceptable Forms of Contraception

Highly effective methods of birth control are defined as those which result in a low failure rate (i.e., less than 1% per year) when used consistently and correctly. These include female sterilization (i.e., documented bilateral tubal ligation), hormonal methods of contraception (oral, implanted, injected, or transdermal) or an IUD in combination with a barrier method (condom, diaphragm). Individually, hormonal, barrier or IUD methods alone are not acceptable.

Acceptable forms of effective contraception are:

- Combined (estrogen and progestogen containing) hormonal contraception associated with inhibition of ovulation (oral, intravaginal, transdermal)
- Progestogen-only hormonal contraception associated with inhibition of ovulation
- Placement of an IUD/ intra-uterine hormone releasing system. Consideration should be given to the type of device or system being used, as there are higher failure rates quoted for certain types, e.g., steel or copper wire
- intrauterine hormone-releasing system (IUS)

The following should be noted:

- Failure rates indicate that, when used alone, the diaphragm and condom are not highly effective forms of contraception. Therefore the use of additional spermicides does confer additional theoretical contraceptive protection
- Spermicides alone are inefficient at preventing pregnancy

7.3.2.4.3 Follow-up in the Event of a Pregnancy

If a female subject, or the female partner of a male subject, who has received K0706 becomes pregnant the pregnancy will be recorded on the Pregnancy Reporting Form. The pregnancy will be communicated to all stakeholders as per the local regulations. The subject will be asked to provide information on the outcome of the pregnancy, including premature termination should the case arise.

Spontaneous miscarriage, maternal/neonatal complications, and congenital abnormalities will be reported as SAEs. The follow-up period will be deemed to have ended when the health status of the child has been determined at birth.

7.3.2.5 Subject Withdrawals

The Investigator will make every reasonable attempt to have the subjects complete the study. However, a subject may withdraw from the study at any time without giving any reason. The Investigator will inform the Sponsor of the withdrawal of any subject.

A subject may be withdrawn in any of the following circumstances:

- Symptomatic or asymptomatic non-haematological Grade 4 toxicity
- Other adverse events such as Grade 3 hematologic/non hematological toxicities [or asymptomatic haematological Grade 4 toxicity hematological toxicities , clearly and incontrovertibly associated with use of K0706 confirmed with bone marrow assessment to delineate disease involvement of the bone marrow] not optimally managed with dose delays and reductions , which in the opinion of the Investigator, can affect overall subject's safety or requires measures which would not allow the continued fulfillment of the protocol requirements and restrictions
- Occurrence of new mutations along with signs/symptoms or laboratory evidence of disease progression
- Non-compliance with study and follow-up procedures
- Entry in another therapeutic clinical trial or start of additional anti-cancer therapy
- Protocol violation
- Pregnancy
- Subject is lost to follow-up
- Subject withdrawal of consent
- Progression of disease
- Termination of the study at Sponsor's discretion including discontinuation of development efforts

The Investigator should as far as possible have the subjects who withdraw complete the assessments at the EoT visit (see Section 11.2). The EoT visit should be completed within 30 days or earlier after withdrawal of the subject. In cases of disease progression, necessitating initiation of an alternative anti-leukemic treatment, the EoT treatment can be completed at an earlier time point within the 30 days after withdrawal of the subject.

- 1) If EoT visit has occurred within 30 days (± 5 days) from last IMP administration and all EoT assessments have been completed, a separate 30 day safety follow-up after last dose should be completed: The decision of using either telephonic discussion/ site visit/medical record review for the 30 day safety follow up will be based upon investigator's assessment of the need basis subject's clinical history and clinical condition.
- 2) If EoT visit has occurred within 30 days (± 5 days) from the last IM administration and all EoT assessments have not been completed, a separate 30 day safety follow-up from the last dose should be completed: In these cases, assessments which have been missed on EoT visit, may be done at the 30 day safety follow-up visit. If based upon investigator's assessment of the subject's clinical history and clinical condition the recommendation is for using either telephonic discussion/medical record review instead of site visit for the 30 day safety, consultation with Sponsor's medical monitor should be sought for the missing EoT parameters.
- 3) If at EoT/30 day safety follow up visit there are any unresolved AEs/SAEs, they will be followed until resolution or until the event is stabilized or until it can be explained by another known cause (i.e. concurrent condition or medication) as per medical judgement of the investigator. The follow up methodology will be based on investigator's discretion and subject's clinical history and clinical condition. Any SAE reported by the patient after the completion of AE collection period and considered related to the study drug should also be reported by the investigator. Disease progression is not considered an AE in this study unless it leads to death or hospitalization in which case it needs to be reported as SAE.

Subjects will continue to be followed for survival.

Subjects who withdraw before first post baseline efficacy assessment in the study will be replaced unless the withdrawal is due to AE related to K0706 or disease progression. All efforts will be taken to keep the subjects withdrawn at $\leq 10\%$ of the proposed sample size per disease cohort.

